4.2 CONCOMITANT THERAPY, RESTRICTIONS, AND RESCUE TREATMENT

4.2.1 Rescue medication, emergency procedures, and additional treatment

Rescue medications to reverse the action of nintedanib or sildenafil are not available.

4.2.1.1 Recommendations for managing AEs (exceptions include diarrhoea and liver enzyme elevations)

- If a patient experiences adverse events considered related to the trial medication, symptomatic treatment should be initiated (e.g. anti-emetic treatment such as dimenhydrinate, if appropriate).
- Patients experiencing adverse events considered related to nintedanib may require drug interruption (up to a maximum of 4 weeks) or reduction of dose (at the discretion of the investigator) to allow for resolution of symptoms.
- After resolution of AE, nintedanib may be reintroduced and/or re-escalated to the higher dose (at the discretion of the investigator):
 - a. If dose has been reduced, consider re-escalation to 150 mg bid
 - b. If treatment was temporarily interrupted, resume treatment at the full dose (150 mg bid), or at the reduced dose (100 mg bid), which subsequently may be re-escalated to the full dose (150 mg bid).
- Patients experiencing adverse events considered related to sildenafil may require drug interruption (up to a maximum of 4 weeks) to allow for resolution of symptoms. No dose adjustments are allowed for sildenafil within this study. In the event of an erection that persists longer than 4 hours, the patient should seek immediate medical assistance.
- For adverse events not related to the trial medications, treatment interruptions for a maximum of 4 weeks are allowed. Nintedanib and sildenafil should then be resumed at the same dose taken prior to interruption.
- In the occurrence of acute IPF exacerbations all treatment options considered adequate by the investigator are allowed.

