1.2.2 Sildenafil

Sildenafil is an inhibitor of cyclic guanosine monophosphate (cGMP) specific phosphodiesterase type-5 (PDE5) in the smooth muscle of the pulmonary vasculature, where PDE5 is responsible for degradation of cGMP. Sildenafil, therefore, increases cGMP within pulmonary vascular smooth muscle cells resulting in relaxation. This can lead to vasodilation of the pulmonary vascular bed and, to a lesser degree, vasodilatation in the systemic circulation.

Sildenafil is rapidly absorbed after oral administration, with a mean absolute bioavailability of 41% (25–63%). Maximum observed plasma concentrations are reached within 30 to 120 minutes (median 60 minutes) of oral dosing in the fasted state. Sildenafil and its major circulating N-desmethyl metabolite are both approximately 96% bound to plasma proteins. Protein binding is independent of total drug concentrations. N-desmethyl metabolite has a phosphodiesterase selectivity profile similar to sildenafil and an in vitro potency for PDE5 approximately 50% of the parent drug. Both sildenafil and the active metabolite have terminal half-lives of about 4 hours. After oral administration, sildenafil is excreted as metabolites predominantly in the faeces (approximately 80% of the administered oral dose) and to a lesser extent in the urine (approximately 13% of the administered oral dose).

Sildenafil metabolism is principally mediated by the CYP3A (major route) and CYP2C9 (minor route) cytochrome P450 isoforms. Therefore, inhibitors of these isoenzymes may reduce sildenafil clearance and inducers of these isoenzymes may increase sildenafil clearance. Concomitant use of sildenafil with ritonavir and other potent CYP3A inhibitors is not recommended.

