Sildenafil is indicated for the treatment of Pulmonary Arterial Hypertension (PAH) in adults to improve exercise ability and delay clinical worsening. The efficacy of sildenafil was evaluated in four phase 3 short term studies (12 to 16 weeks), and included predominately patients with New York Heart Association (NYHA) Functional Class II–III symptoms. Etiologies were idiopathic (71%) or associated with connective tissue disease (25%). Based on the identification of different mechanistic pathways involved in the pathogenesis of pulmonary arterial hypertension, i.e. the nitric oxid, endothelin and prostaglandin pathways, increasing evidence suggests a role for sequential or upfront combination treatment in patients with PAH [[R15-5447](#)]. However, the effects of combination treatment of sildenafil with endothelin antagonists like macicentan or bosentan on morbidity and mortality are mixed [[R15-5445](#); [R15-5446](#)].

Sildenafil (20 mg tid) has also been studied in a 12 week double-blind placebo-controlled randomized trial followed by a 12 week period of open-label treatment which enrolled 180 IPF patients with advanced lung function impairment (STEP-IPF). Although this study met significant differences in some secondary endpoints such as quality of life, it failed to meet its primary outcome of change in 6-minute walk distance of $\geq 20\%$ at week 12 [[R12-3686](#)].

Safety data of sildenafil in adults were obtained from a 12-week, placebo-controlled clinical study and an open-label extension study in 277 patients with PAH, WHO Group I. The overall frequency of discontinuation in patients treated with sildenafil on 20 mg three times a day was 3% and was the same for the placebo group. Most common adverse reactions greater than or equal to 3% and more frequent than placebo were epistaxis, headache, dyspepsia,

flushing, insomnia, erythema, dyspnea, and rhinitis. Adverse reactions were generally transient and mild to moderate in nature.

Potential risks of treatment with sildenafil include hypotension, worsening of pulmonary veno-occlusive disease, epistaxis, visual loss, hearing loss, priapism and vaso-occlusive crisis in patients with pulmonary hypertension secondary to sickle cell disease.

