In the STEP-IPF study approximately 90% of patients in each group (sildenafil or placebo) had at least one adverse event with the most common being dyspnoea, cough and progression of IPF during the double-blind 12 weeks period. The proportion of serious adverse events was also similar between groups (15% in sildenafil vs. 16% in placebo) without significant between-group differences in the occurrence of specific serious adverse events [[R12-3686](#)].

Sildenafil is also indicated in adult men with erectile dysfunction with a recommended dose of 50 mg taken as needed approximately one hour before sexual activity. This dose will not be used in this study.

For a more detailed description of the drug profile refer to the current local Prescribing Information or Summary of Product Characteristics which is included in the Investigator Site File (ISF).

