3.3.4 Removal of patients from therapy or assessments

3.3.4.1 Removal of individual patients

An individual patient is to be withdrawn from trial participation if the patient withdraws consent for trial participation, without the need to justify the decision.

An individual patient is to be withdrawn from all trial drugs (nintedanib and sildenafil/matching placebo) if:

- The patient withdraws consent for study treatment, without the need to justify the decision;
- The patient needs to take concomitant drugs that interfere with the investigational products ([section 4.2.2](#));
- The patient can no longer be treated with trial medication for other medical reasons (such as surgery, adverse events, other diseases, or pregnancy);

If a patient becomes pregnant or pregnancy is suspected during the trial, the patient will be permanently discontinued from study treatment and will be followed up until birth or otherwise termination of pregnancy, please see [section 5.3.7](#).

- The patient experiences signs or symptoms of acute myocardial ischemia or stroke;
- The patient experiences signs of hepatic injury, defined as one of the following:
 - ALT and/or AST \geq 8 fold ULN
 - ALT and/or AST \geq 3 fold ULN and total bilirubin \geq 2 fold ULN
 - ALT and/or AST \geq 3 fold ULN and unexplained INR $>$ 1.5
 - ALT and/or AST \geq 3 fold ULN and unexplained eosinophilia ($>$ 5%)
 - ALT and/or AST \geq 3 fold ULN and appearance of fatigue, nausea, vomiting, right upper abdominal quadrant pain or tenderness, fever and/or rash.

For potential drug induced liver injury (DILI) follow up requirements please see [sections 4.2.1.3](#) and [5.3.6.1](#).

Treatment with nintedanib must be permanently discontinued in the following situations:

- In the opinion of the investigator, the patient experiences unacceptable toxicity due to nintedanib despite dose adjustments and supportive care;
- Gastrointestinal perforation;
- Major surgery including abdominal or intestinal surgery;
- Signs or symptoms of deep vein thrombosis or pulmonary embolism;
- Treatment interruption longer than 4 weeks (continuous).

In addition, permanent discontinuation of nintedanib should be considered in the following situations:

- Patient who requires full dose therapeutic anticoagulation or high dose antiplatelet therapy;
- Increased risk of bleeding (e.g., gross/ frank haemoptysis or haematuria, active gastrointestinal bleeding or ulcers).

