4.2.2 Restrictions

4.2.2.1 Restrictions regarding concomitant treatment

Concomitant medications (or therapy) to provide adequate care may be given as clinically necessary. If restricted concomitant therapy is necessary, treatment with study medication should be permanently discontinued (except in case of acute IPF exacerbations – refer to [section 4.2.1.1](#)).

Table 4.2.2.1:1 Permitted and Restricted Concomitant therapy

	Prior to randomisation	During treatment period	After Visit 7 (Follow-up Period)	After early EOT⁹
Nintedanib	Permitted (150 mg bid dose only)	Study medication	Permitted	Not permitted
Sildenafil	Not permitted in the 4 weeks prior to visit 2 ¹	Study medication	Permitted	Not permitted
Pirfenidone, N-acetylcysteine, Azathioprine, Cyclophosphamide, Cyclosporine	Not permitted in the 4 weeks prior to visit 2 ¹	Not permitted	Not permitted	Permitted
Prednisone and other oral corticosteroid ²	Not permitted in the 4 weeks prior to visit 2 ¹	Not permitted	Not permitted	Permitted

Table 4.2.2.1:1 (continued) Permitted and Restricted Concomitant therapy

Investigational Medication	Not permitted in the 4 weeks prior to visit 2 ¹	Not permitted	Not permitted ¹⁰	Not permitted
Nitrates	Not permitted in the 4 weeks prior to visit 2 ¹	Not permitted	Not permitted	Permitted
Prostaglandins ³ , endothelin-1 antagonists ⁴ or phosphodiesterase inhibitors ⁵ or a stimulator of guanylatcyclase ⁶	Not permitted in the 4 weeks prior to visit 2 ¹	Not permitted	Not permitted	Not permitted
Potent CYP3A4 inhibitors such as ketoconazole, itraconazole and ritonavir	Not permitted in the 4 weeks prior to visit 2 ¹	Not permitted	Not permitted	Permitted
L-arginine, grapefruit juice or St John's wort	Not permitted in the 4 weeks prior to visit 2 ¹	Not permitted	Not permitted	Permitted
Anticoagulation at full dose ⁷ , antiplatelet therapy at high dose ⁸ , fibrinolysis	Permitted	Not permitted	Not permitted	Permitted

1. Washout should not occur until after patient has signed informed consent
2. Prednisone >15 mg daily or >30 mg every 2 days OR equivalent dose of other oral corticosteroids.
3. e.g., epoprostenol, treprostini
4. e.g., bosentan, sitaxsentan, ambrisentan
5. e.g., sildenafil, tadalafil, vardenafil
6. e.g., riociguat

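### In an acute exacerbation the protocol waives its stop rule for restricted drugs, and no rule clearly requires sildenafil/placebo to be held first when an interacting drug is given

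*Protocol*

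**What the plan says.** Protocol Section 4.2.2.1 sets the general rule and its exception together: "If restricted concomitant therapy is necessary, treatment with study medication should be permanently discontinued (except in case of acute IPF exacerbations". The exception refers to Section 4.2.1.1, whose last bullet reads: "In the occurrence of acute IPF exacerbations all treatment options considered adequate by the investigator are allowed". No drug class is named in either place.

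Table 4.2.2.1:1 bars, during the treatment period, nitrates, potent CYP3A4 inhibitors, and a combined row of prostaglandins, endothelin-1 antagonists, phosphodiesterase inhibitors and guanylate cyclase stimulators.

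Section 3.3.4.1 lists reasons for mandatory withdrawal from both trial drugs. One is: "The patient needs to take concomitant drugs that interfere with the investigational products", with a reference to Section 4.2.2. Another is: "The patient can no longer be treated with trial medication for other medical reasons (such as surgery, adverse events, other diseases, or pregnancy". Signs or symptoms of acute myocardial ischaemia or stroke are also on that list. A separate list requires sildenafil/placebo to stop permanently for symptomatic hypotension, or after a continuous interruption of more than 4 weeks.

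On the interaction itself, Section 1.2.2 states that "inhibitors of these isoenzymes may reduce sildenafil clearance" and adds: "Concomitant use of sildenafil with ritonavir and other potent CYP3A inhibitors is not recommended".

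**The concern.** At all other times on treatment, needing a restricted drug ends study medication. In an acute exacerbation that protection is switched off by an express exception, and nothing is put in its place for drugs that may interact with sildenafil. Read literally, an investigator could leave blinded sildenafil/placebo running alongside any of the four classes.

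What is at stake is patient safety. Section 1.2.2 lists hypotension as a potential sildenafil risk. Section 4.2.1 says that no agent is available to reverse the drug's action. Section 4.1.4.2 allows no dose adjustment, so within the protocol a hold is the only measure short of permanent discontinuation.

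The primary analysis is not at stake. No analysis set changes, and SAP Section 7.4.1 already uses observations made after premature discontinuation.

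**Working it through.** **Text check: would any rule require a hold before the interacting drug is given?**

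| Provision | Mandatory? | Acts before co-administration in an exacerbation? |
|---|---|---|
| 4.2.2.1 stop rule | Default is to stop | No; exacerbations are excepted |
| 4.2.1.1 last bullet | Permissive | No; nothing is carved out |
| 3.3.4.1 interfering drugs | Yes | Unclear; it refers to 4.2.2, which contains the exception |
| 3.3.4.1 other medical reasons | Yes, once judged met | Depends on judgement |
| 3.3.4.1 myocardial ischaemia or stroke | Yes | Only where that is the reason for the drug, such as a nitrate for ischaemia |
| 3.3.4.1 symptomatic hypotension | Yes | No; it acts after the event |
| 4.2.1.1 interruption up to 4 weeks | Optional | Only if chosen; resumption is not tied to stopping the other drug |
| 4.1.5.2 emergency unblinding | Optional | Only if chosen |
| SAP Table 6.2:1, C6 and D1 | Recorded as violations | No; they detect and do not hold dosing |

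The 3.3.4.1 bullet on interfering drugs has two readings. If its reference to 4.2.2 imports the exception, which is the more natural reading, no hold follows. If it stands alone, it requires withdrawal and conflicts with the waiver. Both readings call for clearer text.

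**Which classes are affected.** Only potent CYP3A inhibitors have a stated reason (1.2.2). For nitrates, other phosphodiesterase inhibitors and guanylate cyclase stimulators, added vasodilation is inferred from the cGMP mechanism in 1.2.2 and from their barred status. The table does not settle the reason for the last two, because their row stays barred after early end of treatment, when no study drug is taken. Prostaglandins and endothelin-1 antagonists share that row but are left out here. Section 1.2.2 treats them as separate pathways and says that "increasing evidence suggests a role for sequential or upfront combination treatment in patients with PAH".

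**How many exacerbations.** The inputs are 5-10% of IPF patients a year (Section 1.1), 24 weeks of treatment, and 125 patients per arm, 250 in total (synopsis). A constant hazard is assumed and dropout is ignored.

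h = -ln(1 - annual risk); risk to week 24 = 1 - exp(-h × 24/52)

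- 5% a year: h = 0.0513; risk 2.34%; 125 × 0.0234 = 2.9; 250 × 0.0234 = 5.8
- 10% a year: h = 0.1054; risk 4.75%; 125 × 0.0475 = 5.9; 250 × 0.0475 = 11.9
- 20% a year (assumption): h = 0.2231; risk 9.79%; 12.2 of 125; 24.5 of 250

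The sildenafil arm is where an interaction could occur. A blinded hold rule would reach both arms. These are counts of exacerbations, not of co-administrations.

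**Doses lost to a hold.** Planned sildenafil/placebo capsules: 24 × 7 × 3 = 504.

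- 7-day hold (assumption): 7 × 3 = 21; 21/504 = 4.2%
- 28-day hold: 28 × 3 = 84; 84/504 = 16.7%

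**Resumption.** The only interval the protocol gives for these classes is 4 weeks before visit 2 (exclusion criteria 22-24 and the table). Applied after one day of the other drug, it makes the interruption 1 + 28 = 29 days. That exceeds the 4-week limit, so sildenafil/placebo would have to stop permanently. A workable hold rule must therefore say that this washout does not apply.

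**The case against.** A reader might infer that nothing mandatory protects these patients. The documents do not support that. The interfering-drugs bullet in Section 3.3.4.1 is mandatory and carries no exacerbation exception of its own. The ischaemia stop covers nitrates given for that reason. Section 5.2.3 keeps deterioration fully explained by cardiac failure or fluid overload, and extra-parenchymal causes such as pulmonary embolism, outside the definition of an exacerbation. The waiver concerns treatment of the exacerbation, not barred drugs given for something else.

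A reader might also infer that dangerous co-administration is expected. That is not supported either. Nothing in the documents says that any of the four classes is used to treat an exacerbation; freeing corticosteroids and immunosuppressants is the more obvious purpose of the waiver. Section 1.2.2 says not recommended, not contraindicated, and only for CYP3A inhibitors. The absence of a reversal agent does not mean that hypotension cannot be treated, since Section 4.2.1.1 provides for symptomatic treatment.

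Other controls exist. Sites are specialised referral centres (3.1.1). For the drug profile, investigators are told to "refer to the current local Prescribing Information or Summary of Product Characteristics which is included in the Investigator Site File (ISF". A DMC reviews unblinded safety data. Violation D1 captures prohibited therapy with no exacerbation exception.

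All of this stands, and it limits the size of the point. It does not remove the point. The controls either depend on judgement, act after the event, or rest on a cross-reference that leads back to the exception.

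**Conclusion.** The point holds as a cheap improvement for patient safety. An express exception removes the stop rule during an exacerbation, and no provision clearly requires sildenafil/placebo to be held before an interacting drug is given. Section 3.3.4.1 is ambiguous on this, not silent.

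Exposure is unknown and may be zero. The base is about 3-6 exacerbations among 125 sildenafil patients at 5-10% a year, or about 12 at an assumed 20%. That range rests on a general IPF rate. Advanced disease could raise it; background nintedanib, which reduced first exacerbations in two of three trials (Section 2.3), could lower it. The share of these patients given one of the four classes is not in the documents.

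Confidence is highest for potent CYP3A inhibitors, where the protocol states the interaction. For the other three classes the conclusion depends on the mechanistic inference.

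**What to change.** Add to the last bullet of Section 4.2.1.1, and as a new footnote 11 to the matching rows of Table 4.2.2.1:1 in the treatment-period column:

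> If a nitrate, potent CYP3A4 inhibitor, guanylate cyclase stimulator or other phosphodiesterase inhibitor is needed for an acute IPF exacerbation, sildenafil/matching placebo must be interrupted while that drug is given, starting before the first dose where possible, and may be resumed once it has been stopped and the interval the investigator judges adequate from the product labels has passed. The 4-week pre-randomisation washout does not apply. If the interruption exceeds 4 weeks, sildenafil/matching placebo is permanently discontinued (section 3.3.4.1).

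In the Section 3.3.4.1 bullet on interfering drugs, add: *for acute IPF exacerbations see section 4.2.1.1*.

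The rule is the same in both arms, so it needs no unblinding. Nintedanib and all other exacerbation treatments stay as written. There is a precedent: the liver-enzyme table in Section 4.2.1.3 already orders sildenafil interruption under set conditions.

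The cost is a few sentences, one footnote and one cross-reference, with no SAP change and no extra patients, visits or procedures. The downside is missed sildenafil/placebo doses, and occasional permanent discontinuation, in a small number of patients.

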4.2.1.2 Recommendations for managing diarrhoea

In general, diarrhoea should be managed as early as possible after onset of first symptoms with standard antidiarrheal symptomatic treatment, e.g. loperamide.

If diarrhoea persists despite optimal symptomatic treatment, treatment interruption (for a maximum of 4 weeks) and dose reduction of nintedanib should be considered based on the recommendations described in [Table 4.2.1.2: 1](#).

If diarrhoea is not manageable after dose reduction and/or nintedanib interruption, interruption of sildenafil should also be considered.

Table 4.2.1.2: 1 Recommendations for managing diarrhoea

CTCAE Grade	Description	Symptomatic Treatment	Action with Nintedanib
1	Increase of <4 stools per day over baseline	Initiate anti-diarrheal medicines at first signs of symptoms (e.g., 4 mg loperamide followed by 2 mg after each loose stool or every 2-4 hours to a maximum of 16 mg/day ¹) until bowel movements cease for 12 hours	Continue same nintedanib dose
2	Increase of 4-6 stools per day over baseline	Initiate/continue anti-diarrheal medicines; If diarrhoea grade 2 persists for ≥48-72 hours assess for dehydration and electrolyte imbalance; In addition, consider i.v. fluids and electrolyte replacement as clinically indicated.	If diarrhoea grade 2 persists for ≥48-72 hours despite optimal symptomatic care: Interrupt nintedanib until recovery ² Reduce dose to 100 mg bid after recovery Re-escalate to 150 mg bid if deemed clinically appropriate
3 Or 4	Increase of ≥ 7 stools per day over baseline; incontinence; Or Life threatening consequences	Follow recommendations above. In addition, consider stool work-up to exclude infectious colitis; aggressive i.v. fluid replacement ≥24 hours, hospitalisation as clinically indicated; consider referral to a GI specialist to rule out potential differential diagnoses.	Interrupt nintedanib until recovery ² Reduce dose to 100 mg bid after recovery Consider re-escalation to 150 mg bid if deemed clinically appropriate In case of recurrence of diarrhoea grades 3 or 4 despite optimal symptomatic treatment and dose reduction, treatment with nintedanib should be permanently discontinued.

¹ Refer to national prescribing information

² Treatment interruptions are allowed up to a maximum of 4 weeks.

4.2.1.3 Recommendations for managing liver enzyme elevations

For a detailed guidance on how to manage liver enzyme elevations, please refer to table 4.2.1.3: 1

Table 4.2.1.3: 1 Recommendations for managing liver enzyme elevations

AST /ALT ≥ 3 but < 5 x ULN		AST /ALT ≥ 5 but < 8 x ULN		Signs of hepatic injury ³
Reduce nintedanib to 100 mg bid or interrupt ² (at the discretion of the investigator) Lab tests ¹ at 48/72 hours, at 1 week and at 2 weeks		Interrupt ² nintedanib Lab tests ¹ at 48/72 hours, at 1 week and at 2 weeks		Permanently discontinue all study drugs
If AST /ALT < 3 x ULN within 2 weeks	If AST /ALT ≥ 3 ULN at 2 weeks	If AST /ALT < 3 x ULN within 2 weeks	If AST /ALT ≥ 3 ULN at 2 weeks	
Re-escalate nintedanib to 150 mg bid if reduced; restart at 100 mg bid if interrupted Lab tests ¹ at weeks 2 and 4	Interrupt ² both drugs Lab tests ¹ at weeks 1 and 2	Reintroduce nintedanib at 100 mg bid Lab tests ¹ at weeks 1, 2 and 4	Interrupt ² sildenafil Lab tests ¹ at weeks 1 and 2	
If AST / ALT ≥ 3 x ULN permanently discontinue nintedanib	If AST / ALT < 3 x ULN reintroduce drugs in a stepwise approach; lab tests ¹ every week as needed If AST / ALT ≥ 3 x ULN permanently discontinue all study drugs	If AST / ALT ≥ 3 x ULN permanently discontinue nintedanib	If AST / ALT < 3 x ULN reintroduce drugs in a stepwise approach; lab tests ¹ every week as needed If AST / ALT ≥ 3 x ULN permanently discontinue all study drugs	

¹ Laboratory tests include ALT, AST, total bilirubin, eosinophils, INR

² Treatment interruptions are allowed up to a maximum of 4 weeks.

³ Signs of hepatic injury are defined as:

- ALT and/or AST \geq 8 fold ULN
- ALT and/or AST \geq 3 fold ULN and total bilirubin \geq 2 fold ULN
- ALT and/or AST \geq 3 fold ULN and unexplained INR $>$ 1.5
- ALT and/or AST \geq 3 fold ULN and unexplained eosinophilia ($>$ 5%)
- ALT and/or AST \geq 3 fold ULN and appearance of fatigue, nausea, vomiting, right upper abdominal quadrant pain or tenderness, fever and/or rash.

For potential drug induced liver injury (DILI) follow up requirements please see [section 5.3.6.1](#).

